well as any necessary covariates, including cocaine positive vs negative urine tests prior to random assignment as a covariate. Generalized linear mixed models (GLMM) will be used to analyze repeated measures data, since this technique can include participants with incomplete data without resorting to imputation. This approach has been found to minimize bias and maximize power in cases of incomplete follow-up (see Hedden et al, 2009). Data will then be examined using the nonbinary method described by McCann and Li (2012) in which participants who meet an end of study threshold of success (1 week EOS abstinence) are assigned values indicating their number of beyond threshold weeks of success (in our case 1-24). This distribution will be analyzed as a function of drug condition using a two-sided Vander Waerden two-sample test (Permutt and Berger, 2000).

All other analyses will be conducted in the overarching group that includes those abstinent and actively using at baseline. This approach will allow us to preserve all study Aims with a reduced sample size that will ensure the study can be completed in the time allowed.

The data analysis plan consists of the following:

- 1) Comparison of groups for baseline differences. Participants will be compared as a function of medication group on baseline characteristics to determine whether they are comparable with respect to general demographic features, baseline drug use, and reinforcement measures (drug vs. money relative reinforcing potency scale, Snaith-Hamilton Pleasure scale). Groups will be compared using t tests for continuous measures and chi-square tests for categorical characteristics. If medication groups are found to differ on baseline measures, then these characteristics will be used as covariates in subsequent analyses assessing treatment effect.
 - 2) Primary outcome analyses: (see above)
- 3) Secondary outcome analyses: The main secondary outcome measure will be biochemically-confirmed abstinence from opiates. We hypothesize that participants receiving bupropion will have a higher proportion of opiate abstinent samples as well as for cocaine. Analyses conducted to assess the treatment effect for opiate use will be identical to those used for cocaine use (described above).

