- 4) Other Secondary Outcome Analyses: Other secondary outcomes are reinforcement measures, such as the drug vs. money relative reinforcing potency scale, the Snaith-Hamilton Pleasure scale, as well as time engaging in non-drug-related activities and changes in neurocognitive performance. These measures will be collected at baseline and throughout the study. Analyses will be the same as those described for cocaine (GEE with medication group X time as factors). Participants receiving bupropion are hypothesized to find non-drug activities to be more reinforcing than participants receiving placebo, and to engage in more of them.
- 5) Exploratory mediation analysis. Measures collected at baseline including demographic characteristics, intake drug use severity, non-drug reinforcement, non-drug activities and neurocognitive performance will be examined separately to determine whether any predicts outcome independently of treatment. Next, we will add each of these measures to the models that assessed treatment effect, used for primary outcome analyses. If the treatment effect becomes diminished by addition of a third variable, this will be considered preliminary evidence that the third variable may mediate the effect of the treatment.

7. Risks

- a. Medical risks, listing all procedures, their major and minor risks and expected frequency.
- b. Steps taken to minimize the risks.
- c. Plan for reporting unanticipated problems or study deviations.
- d. Legal risks such as the risks that would be associated with breach of confidentiality.
- e. Financial risks to the participants.

Bupropion XL is an FDA-approved antidepressant and smoking cessation pharmacotherapy and will be used in accordance with the prescription labeling instructions during this study. The extended release (XL) preparation allows for once-daily dosing and thus improved adherence. The medication will be titrated to an oral dose of 300 mg after 3 days at 150 mg daily. With a half-life of 21 hours, steady state is

reached after 8 days. Methadone maintenance is a long-standing and effective usual care treatment for opioid dependence but does not directly impact the concurrent use of stimulants alcohol or other drugs.

Risks associated with Bupropion XL side-effects

Major risks of bupropion are summarized below; a complete list of potential side-effects is included in the consent form.

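### Covariates for the secondary outcomes are chosen by baseline imbalance between arms, and no outcome's own baseline is named, which costs precision

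*Combined protocol and SAP*

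**What the plan says.** All of the relevant text is in Section 6, Study Statistics.

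- **Primary cocaine model.** It has medication, time and their interaction, plus "any necessary covariates, including cocaine positive vs negative urine tests prior to random assignment as a covariate". No rule says which covariates count as necessary.
- **Item 1 (baseline comparison).** The measures listed are "general demographic features, baseline drug use, and reinforcement measures (drug vs. money relative reinforcing potency scale, Snaith-Hamilton Pleasure scale"). On testing: "Groups will be compared using t tests for continuous measures and chi-square tests for categorical characteristics". No significance level is given. The consequence is "If medication groups are found to differ on baseline measures, then these characteristics will be used as covariates in subsequent analyses assessing treatment effect".
- **Item 3 (opiates, the main secondary outcome).** "Analyses conducted to assess the treatment effect for opiate use will be identical to those used for cocaine use".
- **Item 4 (choice scale, pleasure scale, activities and "changes in neurocognitive performance").** "These measures will be collected at baseline and throughout the study". The analysis is given as "Analyses will be the same as those described for cocaine (GEE with medication group X time as factors"). No own-baseline term appears.
- **Item 5 (exploratory mediation).** Baseline measures are screened as predictors and added to models, but only to the primary-outcome models.

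Section 4 (Stratification and Random Assignment) randomises within responder and non-responder strata, defined by six consecutive cocaine-negative samples in the lead-in. The rationale in Section 6 speaks instead of the urine result at presentation. The plan does not say whether the urine covariate is the randomisation stratum.

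**The concern.** A covariate earns its place by predicting the outcome. Under randomisation, a tested difference between arms is a chance event unrelated to that. A strongly prognostic baseline will nearly always be left out, and a useless one gets in just as often. The covariate set is also not fixed until the arms have been compared.

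The outcomes most exposed are the continuous ones in item 4. They carry the proposed mechanism (objective c) or are exploratory (objective e), with about 50 participants per arm. Activities and cognition are not in item 1's list, so read literally the rule never reaches their baselines.

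Item 4 also leaves open whether baseline is a covariate or one level of time. The group-by-time wording and the reference to changes in cognition fit the second reading, under which the treatment effect is a change contrast. For opiates, an identical analysis could mean adjusting for pre-randomisation cocaine urine or for opiate urine.

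**Working it through.** **The plan's figure.** Section 6 gives 50 per medication group, for the abstinence question. It states no effect size, alpha or power, so the figure cannot be reproduced, and nothing is given for the scales. For scale only: at two-sided 5% and 80% power, 50 per arm detects (1.960 + 0.842) × √(2/50) = 0.56 SD. That effect is used below as an assumption.

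**How often the rule admits a baseline.** At an assumed 5% test level the probability is 5%, whatever the correlation *r* between baseline and outcome. Stratified randomisation lowers it for baselines related to the stratum: simulated 3.2% at a correlation of 0.4 with the stratum and 2.4% at 0.5.

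**Closed form, one visit, 50 per arm, no attrition.** Residual variance in SD² units is 1 for follow-up only, 2(1 − r) for change from baseline, and 1 − r² with own baseline as covariate.

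| r | Variance: follow-up / change / adjusted | Power at 0.56 SD | Unadjusted n per arm equivalent to 50 adjusted, 50/(1 − r²) |
|---|---|---|---|
| 0.3 | 1 / 1.40 / 0.91 | 80.0 / 65.8 / 83.6% | 55 |
| 0.5 | 1 / 1.00 / 0.75 | 80.0 / 80.0 / 89.9% | 67 |
| 0.7 | 1 / 0.60 / 0.51 | 80.0 / 95.1 / 97.5% | 98 |

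**Simulation of the rule itself.** 40,000 trials per cell, stratum split 25/25 in each arm, 0.56 SD. Monte Carlo error near 80% power is √(0.8 × 0.2/40,000), or 0.2 points. Power (%):

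| Urine stratum | Analysis | r = 0.2 | 0.3 | 0.5 | 0.7 |
|---|---|---|---|---|---|
| Not carried over, or not prognostic | Item 1 rule | 79.2 | 79.2 | 80.2 | 81.4 |
| | Own baseline always | 80.4 | 82.2 | 88.8 | 97.2 |
| In model, correlation 0.2 with outcome and baseline | Item 1 rule | 80.7 | 81.2 | 82.0 | 82.8 |
| | Own baseline always | 81.4 | 83.5 | 89.7 | 97.2 |
| In model, correlation 0.4 with both | Item 1 rule | 85.1 | 85.9 | 86.2 | 86.8 |
| | Own baseline always | 84.9 | 86.5 | 90.9 | 97.4 |
| Baseline as a level of time (stratum correlation 0.2) | Change contrast | 59.1 | 65.4 | 79.2 | 94.7 |

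The gain at r = 0.5 is 8.6, 7.7 and 4.7 points in the three settings. At r = 0.2 it is 1.2, 0.7 and −0.2.

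**Type I error.** Under the rule it is 3.8-4.9% with the stratum in the model, so there is no inflation. Leaving out a stratum correlated 0.4 with the outcome gives 3.2-3.3% type I error and 81-82% power, against 85-86% power with it in.

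**Mean of five follow-up visits, equal correlations.** The variances are (1 + 4r)/5 for follow-up only, that minus r² adjusted, and that plus 1 − 2r for change. At r = 0.3, 0.5 and 0.7 the unadjusted analysis needs 1.26, 1.71 and 2.81 times the sample of the adjusted one. The change analysis needs 2.40, 1.71 and 1.33 times.

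**Opiates, one visit, logistic model.** 20,000 trials per cell, about 50% baseline prevalence, all inputs assumed. Adding baseline opiate status to cocaine urine raises power by about 1-2, 3-4 and 8-9 points when its odds ratio with the outcome is 3, 5 and 10. If the plan already means opiate urine, nothing is lost.

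**The case against.** The strongest reply is that this is an efficiency point on secondary outcomes and may be small. The study-entry baseline precedes up to six weeks of lead-in, so low correlations may be the realistic ones. At r = 0.2 to 0.3 the gain over the rule is 0 to 3 points. That stands.

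The effect size and entry threshold are also assumptions. With no urine effect, the gains at r = 0.2/0.3/0.5/0.7 are 0.3/0.7/1.5/1.5 points at 0.8 SD and about 1/2/9/22 points at 0.3 SD. An entry threshold of 0.20 cuts the gain at r = 0.5 from about 9 to 6.5 points. These change the size, not the direction. The power figures are for a single visit without attrition, so they do not estimate the planned repeated-measures analysis; the five-visit variances show the same ordering at r = 0.3 and 0.5, and adjustment is also best at 0.7.

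The plan is also more open than it first appears. The unspecified allowance for necessary covariates could carry into item 4, and the item 1 rule could be read as covering any baseline measure, including activities and cognition. But an open allowance is not a specification, and the one stated rule still selects on imbalance. Nor is prognosis ignored everywhere: the urine covariate is justified as predictive, and item 5 screens for predictors. Neither supplies the item 4 outcomes with their own baselines.

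Finally, group-by-time may already use baseline. If so, the change contrast falls below adjustment at every correlation examined, and by most when the correlation is low. Only a model with a common baseline mean for both arms would avoid the loss, and none is described.

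**Conclusion.** The concern holds. The stated rule selects covariates on chance imbalance, and the secondary models name no own-baseline term although the data are collected. The consequence is lost precision, mainly on the continuous outcomes of item 4. There is no bias and no type I inflation, and the primary cocaine model is little affected.

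The size cannot be fixed from the documents, which give no correlations or effect sizes. Under the stated assumptions it runs from nothing at r = 0.2 to 5-9 points at r = 0.5 and 11-16 points at r = 0.7. If baseline is treated as a level of time, the shortfall against adjustment is about 21-26 points at r = 0.2 and 3 points at r = 0.7. The change is worth making because it is nearly free, not because the trial's conclusions depend on it.

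**What to change.** Make the item 1 comparison descriptive and delete the imbalance-triggered entry rule. Replace the open allowance for necessary covariates with a named list for each model:

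1. The responder/non-responder randomisation stratum. Add a phrase saying whether the planned cocaine urine covariate is that stratum, so that the two are not entered redundantly.
2. The outcome's own baseline, as a covariate and not a level of time: baseline opiate urine for opiates, and the baseline score for the scales, activities and cognition.

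Define own baseline as the study-entry assessment. Week 6 will not serve, because Section 4 lets responders be randomised from week 3, which makes their week 6 value post-randomisation. As a minor point, reconcile GEE in item 4 with the GLMM named for the cocaine analysis.

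The cost is SAP wording and one or two degrees of freedom per model. The scale, activity and cognitive baselines are already collected. The screening urine tests for cocaine and other drugs, which is assumed here to include opiates.

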Voucher redemption. Throughout the study, participants will be regularly updated on the amount of money in their voucher account. Once earned, voucher money is never taken away. Participants will be able to trade in vouchers at any time for a variety of tangible items and gift cards that will be kept on-site, to request that specific items be brought in for immediate trade-in or to save their voucher money for larger items that will be redeemed at a later time. The only restriction is on purchase of weapons, cigarettes or alcohol.

Contingency management summary. In addition to the schedules outlined above, participants will be reinforced for attendance of the short-assessment visit which occurs once-weekly. Participants can earn 1 bus token (good for a one-way trip) each time they attend and complete the short assessment. Participants may also receive other incentives for session attendance. The abstinence reinforcement schedules developed for this study are specially tailored to the study questions and subpopulations being addressed. Those who can stop their cocaine use before receiving medication may have higher dopamine function than those who do not (Martinez et al., 2011) but may still benefit from a dopamine-boosting medication for delaying or circumventing relapse. Their CM schedule, that incorporates a decelerating payment phase, is tailored for a time-to relapse assessment. In those who struggle to initiate abstinence, the escalating CM schedule will provide an appropriate background for detecting reinforcer boosting effects of a dopaminergic medication.

Study Measures (all but standard screening tools are appended in application)

Screening measures. Screening for stimulant and alcohol use disorders will be conducted using the DSM-5 checklist (American Psychiatric Association, 2013). Psychiatric screening will be conducted using the MINI International Neuropsychiatric Interview (Sheehan et al., 1998), a validated instrument that yields psychiatric diagnoses based on DSM-IV criteria. We will not administer the entire instrument. Rather, it will be used to screen for current major depression, mania/hypomania, psychosis, eating disorders and suicidality. We will continue to employ the Beck Depression Inventory as a measure of depressed mood and will conduct urine screen for cocaine and other drugs.

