The aim of this study is to evaluate whether bupropion will enhance cocaine abstinence among methadone-maintained patients who are abusing cocaine. This is being evaluated in a double-blind context. Further, based on evidence that individuals with cocaine use disorder typically present to the clinic with a urine sample that is positive for cocaine (which predicts continued use) or negative for cocaine (which predicts abstinence), we had originally proposed to treat those individuals as two separate groups and run 2 parallel studies (presented as Primary Aims 1 and 2), using contingency management as a background platform to support either abstinence or relapse prevention, respectively. Each aim was intended to enroll 100 individuals (N=200) total, to enable equal distribution of bupropion (n=50) and placebo (n=50) within each aim.

Based on unanticipated difficulties with recruitment, we are now collapsing the two parallel studies into the same overarching study, such that Primary Aim 1 will now be examining the effects of bupropion XL vs. placebo on 24-week abstinence outcomes during and after exposure to a behavioral intervention (CM). We are reducing our sample size to 100 individuals, which still preserves the required 50 participants per medication group that was identified in our power analyses as necessary to detect an effect of the medication. This approach will allow us to achieve our primary aim of determining whether bupropion will enhance cocaine abstinence despite challenges with recruitment and will enable this study to still provide clinically important information to advance the treatment of cocaine use disorder.

We are modifying our statistical plan to accommodate this change in sample size. We will retain the original primary outcome measure (biochemically-confirmed abstinence from cocaine), which will be assessed across all participants (independent of abstinence group) in the same statistical model. The endpoint will be binary (abstinent yes or no), and the treatment effect will be assessed using a repeated-measures logistic regression model having two main effects: medication and time, plus their interaction, as

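### The opiate analysis copies the cocaine model, so the main secondary outcome has no pre-specified baseline opiate covariate

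*Combined protocol and SAP*

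**What the plan says.** Item 3 of the data analysis plan in Section 6 states: "The main secondary outcome measure will be biochemically-confirmed abstinence from opiates". It adds a directional hypothesis in favour of bupropion and then sets the method: "Analyses conducted to assess the treatment effect for opiate use will be identical to those used for cocaine use (described above".

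The cocaine analysis it points to is a logistic model for repeated urines, with terms for medication, for time and for the interaction of the two. Its covariates are given as an open list with one named member: "well as any necessary covariates, including cocaine positive vs negative urine tests prior to random assignment as a covariate". It is to be fitted as a generalized linear mixed model (GLMM) and followed by a two-sample Van der Waerden test.

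A second route for covariates is item 1, which compares the arms to see "whether they are comparable with respect to general demographic features, baseline drug use, and reinforcement measures". It continues: "If medication groups are found to differ on baseline measures, then these characteristics will be used as covariates in subsequent analyses assessing treatment effect".

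On data, Section 4 (Screening measures) says that staff "will conduct urine screen for cocaine and other drugs", and the weekly assessments list a periodic full drug screen without giving its frequency. Section 4 (Stratification and Random Assignment) stratifies randomisation by response to the lead-in, defined by cocaine-free urines.

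**The concern.** In the cocaine model, the one named covariate is the outcome's own earlier value. Section 6 itself argues that a cocaine urine at presentation predicts later cocaine results. The same reasoning applied to opiates points to the participant's own earlier opiate result. Copying the model across brings the cocaine term but no opiate counterpart.

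Two things are at stake. Leaving out a prognostic baseline value leaves avoidable between-person variance in the test of the main secondary hypothesis. This matters more now that the planned sample has fallen from 200 to 100. Also, a chance imbalance in opiate use is adjusted for only if it is large enough to be detected. Neither makes the randomised comparison invalid.

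**Working it through.** **Inputs.** From Section 6: 100 participants, 50 per arm. Not in the documents, and so assumed: two-sided alpha of 0.05 for the model, opiate rates, number of opiate urines, effect sizes, and the correlation between baseline and later opiate results.

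**The plan's own figure.** The 50 per group is attributed to power analyses, but no alpha, power, effect size or rates are given. It cannot be reproduced or called wrong, and no power figure is given for opiates. It serves here only as the sample size.

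**Does the imbalance route close the gap?** Take 50% opiate-positive, a 0.05 threshold and no continuity correction. The smallest difference flagged is 1.96 × sqrt(2 × 0.25/50) = 1.96 × 0.10 = 0.196, about 20 percentage points. Smaller imbalances stay unadjusted. If the arms balance, the covariate stays out and its precision is lost.

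**Closed form for adding the covariate.** Suppose the model without it has 80% power. The detectable standardised difference is (1.960 + 0.842) × sqrt(2/50) = 0.5603. Let ρ be the correlation of the baseline opiate urine with the participant's later opiate-negative proportion, beyond the cocaine covariate. The residual SD becomes sqrt(1 − ρ²), so power = Φ(0.5603/(0.2 × sqrt(1 − ρ²)) − 1.960). The equivalent unadjusted size is 50/(1 − ρ²) per arm. For ρ = 0.5: 0.5603/(0.2 × 0.866) = 3.235; 3.235 − 1.960 = 1.275; Φ = 0.899.

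| ρ | Power | Equivalent n per arm |
|---|---|---|
| 0.1 | 80.4% | 50.5 |
| 0.2 | 81.6% | 52.1 |
| 0.3 | 83.6% | 54.9 |
| 0.4 | 86.4% | 59.5 |
| 0.5 | 89.9% | 66.7 |
| 0.6 | 93.8% | 78.1 |
| 0.7 | 97.5% | 98.0 |

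**Simulation of adding it.** The outcome was random-intercept logistic, with 24 opiate urines per person and one baseline opiate urine. Log-odds effects were 0.7 (SD 1) and 1.3 (SD 2), with 1,500 runs per setting. The analysis was ANCOVA on each participant's proportion, which approximates the GLMM. The correlation between the cocaine stratum's underlying variable and latent opiate use was set at 0, 0.3 and 0.5.

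- SD 1 (ρ about 0.38): cocaine term only 87.9%, 89.1%, 90.5%; both terms 92.1%, 92.7%, 93.5%. Gains are 4.2, 3.6 and 3.0 points.
- SD 2 (ρ about 0.61): cocaine term only 84.5%, 86.8%, 91.4%; both terms 95.9%, 95.9%, 96.7%. Gains are 11.4, 9.1 and 5.3 points.
- Replacing the cocaine term (SD 1, correlation 0.5) gave 90.3% against 90.5%, so no gain. Adding gave 93.5%.

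**Logistic GEE simulation, medication main effect.** Settings were 12 urines, latent cocaine-opiate correlation 0.2, effects 0.6/0.85/1.1 for SD 1.0/1.5/2.0, and 400 runs each. Using the opiate rather than the cocaine baseline moved power from 73.5% to 75.8%, 72.0% to 83.0% and 68.3% to 85.5% (gains of 2.3, 11.0 and 17.2 points). A repeat under the same assumptions gave about 68% to 73%, 81% to 85% and 73% to 91% (5, 4 and 18 points). A further set of 250 runs gave 72% to 82% at SD 1 and 68% to 84% at SD 2 (10 and 16 points). With 400 runs, the Monte Carlo standard error near 72% is sqrt(0.72 × 0.28/400) = 0.022, and starting levels differ between sets by up to 9 points (72% against 81% at SD 1.5). Only the direction and the range should be relied on.

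**Medication-by-time term.** With an effect that grows over time (250 runs), power with the cocaine versus the opiate baseline was 84.8% vs 84.8%, 84.0% vs 83.6% and 86.8% vs 86.8%. A person-level covariate barely affects a within-person contrast.

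**Van der Waerden test.** It is a two-sample test with no covariates, so nothing changes.

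**The case against.** The strongest reply is that the plan is under-specified rather than wrong. The covariate list is open, so an identical opiate analysis inherits that openness and could include baseline opiate status. Item 1 can bring in baseline drug use, and item 5 adds intake drug use severity to the treatment models. This stands in part: nothing excludes the opiate baseline. But a covariate chosen later is not pre-specified, item 1 responds to imbalance rather than prognostic value, and item 5 is exploratory and refers to the primary-outcome models.

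A reader might infer that the cocaine urine is the wrong covariate for opiates and should be replaced. The documents do not support that. Randomisation is stratified on a cocaine-urine criterion, the covariate reflects that stratum, and keeping it in the opiate model is proper. The simulation also shows a setting in which replacement gains nothing.

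Two further objections stand. Section 6 does not say whether the medication main effect or the interaction is the test of treatment, and the gain belongs to the first. Opiate testing before randomisation is inferred: neither urine list names opiates or gives timing. Randomisation falls in week 3 at the earliest, and at the start of week 6 for clear non-responders, so a screening value would be weeks old. The simulations assume a stable underlying level and so overstate its value if it has decayed.

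**Conclusion.** The point holds as a gap in pre-specification that costs precision on the main secondary outcome. Read as written, item 3 fixes the cocaine covariate and leaves baseline opiate status to an open list or to an imbalance test.

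The size cannot be taken from the documents. For the medication main effect, the gain runs from a few points to nearly 20 points of power under assumed between-person SDs of 1.0 to 2.0. It is under 1 point if the correlation is 0.1 or less.

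A reader might also infer that the opiate comparison is biased without this covariate. It is not: randomisation protects it either way. The change is worth making because it is nearly free, not because the present analysis is invalid.

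**What to change.** In Section 6, item 3, replace the reference to an identical analysis with a statement that the opiate GLMM has the same form as the cocaine GLMM, keeps the cocaine or responder-stratum covariate, and adds the last available pre-randomisation opiate urine result (positive or negative), from the lead-in full drug screen or, failing that, the screening urine. State that this covariate is included whatever the observed baseline difference between arms. State also when opiates are tested before randomisation, so that the source of the value is clear.

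The cost is a sentence or two in the plan. If the existing drug screens include opiates, as the outcome definition implies, no new visits or samples are needed.
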